CLINICAL STUDY PROTOCOL

Protocol Number MYK-461-004

Protocol Title: A Phase 2 Open-label Pilot Study to Evaluate Efficacy, Pharmacokinetics, Pharmacodynamics, Safety, and Tolerability of MYK-461 in Subjects With Symptomatic Hypertrophic Cardiomyopathy and Left Ventricular Outflow Tract Obstruction (Pioneer-HCM)

Indication: Hypertrophic Cardiomyopathy

Phase: 2

Investigational Medicinal Product MYK-461

Sponsor: MyoKardia, Inc.
[name]
[name]

Key Sponsor Contacts: [name]
Senior Manager, Clinical Operations
[contact]
[contact]
[name]
Executive Director, Clinical Development
[contact]
[contact]

Original Protocol Date: 12 May 2016

Amendment 1 Date: 01 March 2017

Amendment 2 Date: 05 May 2017

Confidentiality Statement

This document contains trade secrets or otherwise confidential and/or proprietary information of MyoKardia, Inc. Access to and use of this information is strictly limited and controlled by MyoKardia, Inc. Acceptance of this document constitutes agreement by the recipient that the contents will be not be copied, distributed, or otherwise disclosed to third parties, and will not be used in any way, except as expressly authorized by MyoKardia, Inc.

PROTOCOL SYNOPSIS

Protocol Number and Title:

MYK-461-004: A Phase 2 Open-label Pilot Study to Evaluate Efficacy, Pharmacokinetics, Pharmacodynamics, Safety, and Tolerability of MYK-461 in Subjects With Symptomatic Hypertrophic Cardiomyopathy and Left Ventricular Outflow Tract Obstruction (Pioneer-HCM)

Name of Investigational Product: MYK-461

Sponsor: MyoKardia, Inc.

Phase: 2

Study Objectives:**Primary Objective:**

- To characterize the effect of 12 weeks of MYK-461 treatment on reducing post-exercise peak left ventricular outflow tract (LVOT) gradient in subjects with symptomatic hypertrophic cardiomyopathy (HCM) and LVOT obstruction

Secondary Objectives:

- To assess the proportion of subjects achieving an LVOT gradient response of post-exercise peak gradient < 30 mm Hg in subjects with symptomatic HCM and LVOT obstruction
- To assess the effects of 12 weeks of MYK-461 treatment on dyspnea symptom score, peak oxygen uptake (pVO₂), and volume expired (VE)/carbon dioxide production (VCO₂) slope in subjects with symptomatic HCM and LVOT obstruction
- To evaluate the pharmacokinetics (PK) of MYK-461 in subjects with symptomatic HCM and LVOT obstruction
- To evaluate the pharmacodynamics (PD) of MYK-461 in subjects with symptomatic HCM and LVOT obstruction as assessed by a variety of echocardiographic imaging parameters in subjects with symptomatic HCM and LVOT obstruction
- To evaluate the safety and tolerability of MYK-461 in subjects with symptomatic HCM and LVOT obstruction
- To evaluate the posttreatment reversibility of the effects of MYK-461 after 4 weeks of washout in subjects with symptomatic HCM and LVOT obstruction

Exploratory Objectives:

- To assess the proportion of subjects achieving an LVOT gradient response of post-exercise peak gradient < 10 mm Hg in subjects with symptomatic HCM and LVOT obstruction
- To assess the effects of 12 weeks of MYK-461 treatment on New York Heart Association (NYHA) functional class, N-terminal pro B-type natriuretic peptide (NT-proBNP), and the Kansas City Cardiomyopathy Questionnaire (KCCQ) Overall Summary Score (OSS) in subjects with symptomatic HCM and LVOT obstruction
- To assess the effects of MYK-461 treatment on arterial pulse wave morphology assessed using an optical biosensor in subjects with symptomatic HCM and LVOT obstruction
- To assess the effect of MYK-461 treatment on heart rate and heart rhythm as assessed using a cardiac monitoring skin patch in subjects with symptomatic HCM and LVOT obstruction

Eligibility Criteria:**Inclusion Criteria:**

Each subject must meet the following criteria to be included in this study.

1. Able to understand and comply with the study procedures, understand the risks involved in the study, and provide written informed consent according to federal, local, and institutional guidelines before the first study-specific procedure.
2. Men or women 18 to 70 years of age at the Screening visit.
3. Diagnosed with HCM (hypertrophied and non-dilated left ventricle in absence of systemic or other known cause), with left ventricular [LV] wall thickness ≥ 15 mm at time of initial diagnosis or ≥ 13 mm with a positive family history of HCM.
4. Body mass index (BMI) 18 to 37 kg/m², inclusive, at the Screening visit, calculated using the institution's standard formula.
5. All safety laboratory parameters (chemistry, hematology, and urinalysis) within normal limits (laboratory reference range) at the Screening visit as assessed by the central laboratory, or if outside of the limits must meet both of the following criteria:
 - considered by the investigator to be clinically unimportant
 - if a liver function test result, must be $< 1.5 \times$ the upper limit of the laboratory reference range.
6. Has documented left ventricular ejection fraction (LVEF) $\geq 55\%$ at the Screening visit as determined by the investigator and the investigational site's echocardiography laboratory.
7. Resting LVOT gradient ≥ 30 mm Hg and post-exercise peak LVOT gradient ≥ 50 mm Hg at the Screening visit as determined by the investigator and the investigational site's echocardiography laboratory.

8. NYHA functional class II or higher, judged by the investigator to be due to LVOT obstruction.
9. Has adequate acoustic windows, in the judgment of the investigator and the investigational site's echocardiography laboratory, to enable accurate transthoracic echocardiograms (TTEs).
10. Female subjects must not be pregnant or lactating and, if sexually active, must be using one of the following acceptable birth control methods from the Screening visit through 3 months after the last dose of investigational medicinal product (IMP). Hormonal contraceptives are not considered highly effective contraception for this study because MYK-461 could reduce the effectiveness of hormonal contraceptives.
 - Double-barrier method (e.g., vasectomy or male using a condom and female using a diaphragm or cervical cap)
 - Barrier (e.g. male using a condom) plus non-hormonal intrauterine device (IUD) or intrauterine system (IUS)
 - Female is surgically sterile for 6 months or postmenopausal for 2 years. Permanent sterilization includes hysterectomy, bilateral oophorectomy, bilateral salpingectomy, and/or documented bilateral tubal occlusion at least 6 months prior to Screening. Females are considered postmenopausal if they have had amenorrhea for at least 2 years or more following cessation of all exogenous hormonal treatments and follicle-stimulating hormone (FSH) levels are in the postmenopausal range.
11. Male subjects with female partners (including postmenopausal partners) must agree to use highly effective contraceptive measures from the Screening visit through 3 months after the last dose of study medication. Highly effective contraception includes documented vasectomy, abstaining from sexual intercourse, double-barrier method (e.g., male using a condom and female using a diaphragm or cervical cap), or barrier plus hormonal contraception (e.g., male using a condom and female using hormonal contraception). As there may be a risk of drug being secreted in the ejaculate, male subjects (including men who have had vasectomies) whose partners are currently pregnant should use barrier methods for the duration of the study and for 3 months after the last dose of study medication. In addition, male subjects with sexual partners should use condoms for the duration of the study and for 3 months after the last dose of study medication, even if the partner is not pregnant or capable of becoming pregnant, in order to prevent passing MYK-461 to the partner in the ejaculate.
12. Must be able to complete the Dyspnea Numeric Rating Scale (NRS) and the KCCQ per established guidelines.

Exclusion Criteria:

Subjects who meet any of the following criteria will be excluded from the study.

1. Hypersensitivity to MYK-461 or any of the components of the MYK-461 formulation.

2. Presence of any medical condition that precludes exercise stress testing.
3. History of sustained ventricular tachyarrhythmia.
4. History of syncope with exercise within past 6 months.
5. Active infection.
6. Persistent atrial fibrillation or atrial fibrillation at Screening or history of paroxysmal atrial fibrillation with resting rate documented >100 bpm within 1 year of screening.
7. Has QTc Fridericia (QTcF) > 500 ms, or any other electrocardiogram (ECG) abnormality considered by the investigator to pose a risk to subject safety (e.g., second degree atrioventricular block type II).
8. Aortic stenosis or fixed subaortic obstruction.
9. History of LV systolic dysfunction (LVEF < 45%) at any time during their clinical course.
10. History of obstructive coronary artery disease (stenosis of >70% of luminal diameter in one or more coronary arteries).
11. History of malignancy of any type, with the following exceptions: in situ cervical cancer more than 5 years prior to Screening or surgically excised non-melanomatous skin cancers more than 2 years prior to Screening.
12. Positive serologic test at Screening for infection with human immunodeficiency virus (HIV), hepatitis C virus (HCV), or hepatitis B virus (HBV).
13. Positive test for alcohol or drugs of abuse at Screening.
14. History or evidence of any other clinically significant disorder, condition, or disease (with the exception of those outlined above) that, in the opinion of the investigator or MyoKardia physician, would pose a risk to subject safety or interfere with the study evaluation, procedures, or completion.
15. Participated in a clinical trial where the subject received any investigational drug (or is currently using an investigational device) within 30 days prior to Screening, or at least 5 times the respective elimination half-life (whichever is longer).
16. Current use of tobacco- or nicotine-containing products exceeding 10 cigarettes per day or equivalent.
17. Part A: Subjects who in the opinion of the investigator require ongoing therapy with β -blockers, calcium channel blockers, or disopyramide. Subjects on any of these medications who, in the opinion of the investigator, can safely be withdrawn are eligible as long as medication is discontinued at least 14 days prior to the Screening visit.

Part B: Subjects who in the opinion of the investigator require ongoing therapy with calcium channel blockers or disopyramide. Subjects on any of these medications who, in the opinion of the investigator, can safely be withdrawn are eligible as long as medication is discontinued at least 14 days prior to the Screening visit.

18. Prior treatment with cardiotoxic agents such as doxorubicin or similar, or current treatment with antiarrhythmic drugs that have negative inotropic activity, e.g., flecainide or propafenone.
19. Unable to comply with the study restrictions/requirements, including the number of required visits to the clinical site.
20. Is employed by, or is a relative of someone employed by MyoKardia, the investigator, or his/her staff or family.

Study Treatment:

Study medication will consist of MYK-461 immediate-release oral tablets, 2 mg, 5 mg, 10 mg, and 20 mg.

Part A:

Subjects on β -blockers who, in the opinion of the investigator, can safely be withdrawn are eligible for this part of the study as long as medication is discontinued at least 14 days prior to the Screening visit. The starting dose will vary based on individual subjects' weight. Subjects who weigh ≤ 60 kg will start at 10 mg and subjects who weigh > 60 kg will start at 15 mg. Each subject will receive oral MYK-461 at their determined starting dose once daily (QD) beginning on Day 1 and continuing through Week 4. At Week 4, an individual subject's daily dose may be adjusted based on predetermined criteria (see Study Design). The subject will subsequently receive that dose from Week 5 through Week 12.

Part B:

Subjects not currently taking beta blockers and subjects on a stable dose of β -blockers for at least 14 days, who in the opinion of the investigator require ongoing therapy with β -blockers at the same dose, are eligible for this part of the study. This includes patients treated with β -blockers for rate control of paroxysmal atrial fibrillation. The starting dose will be 2 mg MYK-461 QD beginning on Day 1 and continuing through Week 4. At Week 4, an individual subject's daily dose may be adjusted based on predetermined criteria (see Study Design). The subject will subsequently receive that dose from Week 5 through Week 12.

Number of Subjects Planned: Approximately 20 (10 in Part A, 10 in Part B)

Number/Location of Investigational Sites: Approximately 7 sites in the United States

Study Duration: Approximately 18 months

Study Design:

This is a phase 2 open-label pilot study to evaluate the efficacy, PK, PD, safety, and tolerability of MYK-461 in subjects with symptomatic HCM and LVOT obstruction. Approximately 20 adult subjects with symptomatic HCM, a resting LVOT gradient ≥ 30 mm Hg, and post-exercise peak LVOT gradient ≥ 50 mm Hg will be enrolled. The study will have a 12-week treatment phase and a 4-week washout phase.

At Screening, subjects will undergo TTE in the supine or left lateral decubitus position. In addition to a standardized complete TTE, both resting instantaneous peak LVOT gradient (baseline) and provoked peak LVOT gradient (Valsalva maneuver) will be collected. Subjects will then undergo a standard symptom-limited exercise test (hemodynamic stress echocardiography). Subjects will be assessed systematically for symptoms of dyspnea and/or angina. Instantaneous peak LVOT gradient will be assessed immediately post-exercise by TTE.

On Day 1, resting TTE will be performed, blood samples will be drawn for PK, and subjects will have an assessment of pVO₂, VE/VCO₂, and other variables via cardiopulmonary exercise testing (CPET). After CPET, subjects will be dosed with open-label oral MYK-461 at the investigational site and will be observed for at least 1 hour after dosing, with assessment of vital signs and ECGs at 1 hour postdose. Subjects will then be supplied with MYK-461 for QD dosing at home.

Subjects will be evaluated at the investigational site at Weeks 1, 2, 3, 4, 5, 6, 7, 8, 12, and 16. At each of these visits, resting TTE will be performed and blood samples will be drawn for PK. On study visit days, study medication will be administered at the investigational site in order to collect blood samples for PK \leq 2 hours prior to dosing. At Weeks 4, 12, and 16, hemodynamic stress echocardiography will be performed and peak LVOT gradient will be assessed. CPET will be conducted between Weeks 10 and 12 (inclusive).

Part A:

The MYK-461 starting dose will be 10 mg for subjects who weigh \leq 60 kg and 15 mg for subjects who weigh $>$ 60 kg. At the end of Week 4 (Day 28), each subject's LVEF will be evaluated, and the subject's dose may be increased, decreased, or remain unchanged based on the predetermined criteria below, in consultation between the investigator and the medical monitor. If MYK-461 plasma concentration exceeds 750 ng/mL at Week 2, no dose increase is allowed, regardless of LVEF data at Week 4; however, dose decrease per LVEF data is allowed in this circumstance. The subject will subsequently receive that dose from Week 5 through Week 12.

Percent Decrease From Baseline in LVEF at the End of Week 4 (Day 28)	Action for MYK-461 Dose Week 5-Week 12^a
< 10	increase dose by 10 mg
\geq 10 and < 15	increase dose by 5 mg
\geq 15 and < 20	no change in dose
\geq 20	decrease dose by 5 mg

^a LVEF, left ventricular ejection fraction No dose increase allowed if plasma concentration of MYK-461 $>$ 750 ng/mL at Week 2.

Part B:

The MYK-461 starting dose will be 2 mg. At the end of Week 4 (Day 28), each subject's resting (non-provoked) peak instantaneous LVOT gradient and LVEF from the Week 4 TTE will be evaluated. The subject's dose will be increased to 5 mg or remain unchanged based on the predetermined criteria below, in consultation between the investigator and the medical monitor. If MYK-461 plasma concentration exceeds 300 ng/mL at Week 2, no dose increase is allowed. The subject will subsequently receive that dose from Week 5 (Day 29) through Week 12.

Percent Decrease From Day 1 in Resting TTE Instantaneous Peak LVOT gradient at the End of Week 4 (Day 28)	Action for MYK-461 Dose Week 5-Week 12^a
< 50%	increase dose to 5 mg
≥ 50%	no change in dose

^a LVOT, left ventricular outflow tract; TTE, transthoracic echocardiogram; No dose increase allowed if plasma concentration of MYK-461 > 300 ng/mL at Week 2.

For all subjects who provide consent, blood will be drawn prior to dosing on Day 1 for assessment of HCM genotype and potentially additional deoxyribonucleic acid (DNA) sequencing.

In addition, subjects may consent separately to collection of pharmacogenetic samples that will be stored for potential future analysis of genetic biomarkers of efficacy, safety-related, PD, or PK parameters as determined by future studies using clinically meaningful endpoints, through DNA sequencing or other genetic testing.

Blood samples will be collected from all subjects prior to dosing on Day 1 and at Week 12 and stored for exploratory circulating biomarker analysis, e.g., proteomic analysis related to disease activity, metabolic pathways, efficacy measures, or safety measures.

Study Assessments and Procedures:

The efficacy of MYK-461 will be evaluated using TTE and CPET. The primary endpoint will be the change from baseline to Week 12 in post-exercise peak LVOT gradient.

Secondary endpoints include the proportion of subjects achieving a LVOT gradient response of post-exercise peak gradient < 30 mm Hg; change from baseline to Week 12 in the dyspnea symptom score, pVO₂, VE/VCO₂, LVEF (2-dimensional [2D] and 3-dimensional [3D]), global longitudinal strain, and left ventricular fractional shortening (LVFS); and change from Week 12 to Week 16 in post-exercise peak LVOT gradient. The plasma PK profile of MYK-461 is also a secondary endpoint.

Exploratory endpoints include the proportion of subjects achieving an LVOT gradient response of post-exercise peak gradient < 10 mm Hg; change from baseline to Week 12 in NYHA functional class, NT-proBNP, and KCCQ OSS; change from baseline in arterial pulse wave morphology assessed using an optical biosensor; and change from baseline in heart rate and heart rhythm as assessed using a cardiac monitoring skin patch.

Safety endpoints include treatment-emergent AEs and serious adverse events (SAEs), and changes from baseline in laboratory test results, vital signs, and ECGs. Any abnormal ECG or vital sign finding judged by the investigator to be clinically important will be recorded as an AE.

End of Study

Subjects will be followed through completion of End of Study (EOS) procedures. All AEs, including SAEs and deaths, will be collected for the duration of the study, up to and including the EOS visit.

If there is a significant clinical abnormality or a clinically significant laboratory abnormality in need of monitoring, the subject will be followed until resolution of the abnormality or until it is considered stable in the opinion of the investigator.

Sample Size and Statistical Considerations:

Sample Size:

Approximately 10 subjects will be dosed in Part A and approximately 10 in Part B. The sample size is based on practical considerations and is consistent with this type of study. Ten subjects receiving MYK-461 will provide 80% power to detect a 30 mm Hg difference versus baseline in post-exercise LVOT peak gradient and a > 99% power to detect a 50 mm Hg difference. This assumes a 1-sided $\alpha = 0.05$ and a common standard deviation of 35 mm Hg.

Statistical Analyses:

All efficacy and PD analyses will be performed on the Efficacy/PD Analysis Population, which comprises all subjects who receive at least 1 dose of MYK-461 and have primary or secondary endpoint data, including a baseline value and at least one post baseline value measured during the on-treatment period.

Post-exercise peak LVOT gradient will be analyzed using a mixed-effect model with repeated measures (MMRM). All data available from baseline (Screening) to Week 16 (EOS) will be included and missing data will be accounted for by the MMRM model. The model will include the fixed categorical effects of timepoint: baseline Week 4, Week 12 (end of treatment), and Week 16 (EOS). This model will provide least-squares (LS) mean estimates with their corresponding standard errors at each time point. Comparison between baseline and Week 12 (end of treatment) will be based on the LS mean difference obtained from the MMRM, and will be presented with its associated 95% confidence interval. Statistical significance of the difference versus baseline will be evaluated at the 1-sided 0.05 level.

The proportion of subjects achieving LVOT gradient responses of < 30 mm Hg and < 10 mm Hg will be summarized at each post-baseline visit. In case of missing data at a given visit, it will be assumed that the subject had not achieved an LVOT gradient response. Quantitative endpoints, including the Dyspnea NRS, pVO₂, VE/CO₂, LVEF, NYHA functional classification, NT-proBNP, and KCCQ OSS will be analyzed using the same

MMRM model as for the primary efficacy endpoint. The list of timepoints included in the MMRM will be adjusted according to the visits at which each endpoint will be measured. Data collected from the optical biosensor and cardiac monitoring skin patch will be analyzed descriptively.

Plasma concentrations of MYK-461 will be determined and summarized descriptively.

TABLE OF CONTENTS

CLINICAL STUDY PROTOCOL 1

PROTOCOL SYNOPSIS 2

TABLE OF CONTENTS..... 11

LIST OF TABLES 15

LIST OF FIGURES 15

LIST OF APPENDICES..... 15

LIST OF ABBREVIATIONS..... 16

1 INTRODUCTION 18

 1.1 Background 18

 1.2 Clinical Studies 18

 1.2.1 MYK-461-002 19

 1.2.2 MYK-461-001 19

 1.2.3 MYK-461-003 19

 1.3 Known and Potential Benefits and Risks 20

2 RATIONALE FOR THE STUDY AND FOR DOSE AND DOSING SCHEDULE 21

 2.1 Rationale for the Study 21

 2.2 Rationale for Dose and Dosing Schedule 21

3 STUDY OBJECTIVES 22

 3.1 Primary Objective 22

 3.2 Secondary Objectives 22

 3.3 Exploratory Objectives 22

4 OVERALL STUDY DESIGN AND PLAN 23

 4.1 Study Duration 25

 4.2 Independent Data Monitoring Committee 25

5 SELECTION AND WITHDRAWAL OF STUDY POPULATION 26

 5.1 General Study Population and Clinical Sites 26

 5.2 Inclusion Criteria 26

 5.3 Exclusion Criteria 27

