4 OVERALL STUDY DESIGN AND PLAN

This is a phase 2 open-label pilot study to evaluate the efficacy, PK, PD, safety, and tolerability of MYK-461 in subjects with symptomatic HCM and LVOT obstruction. Approximately 20 adult subjects with symptomatic HCM, a resting LVOT gradient ≥ 30 mm Hg, and post-exercise peak LVOT gradient ≥ 50 mm Hg will be enrolled. Approximately 10 subjects will participate in Part A and approximately 10 subjects will participate in Part B. The study will have a 12-week treatment phase and a 4-week washout phase (Figure 1).

Figure 1 Study Schema

CPET, cardiopulmonary exercise training; D, day; HSE, hemodynamic stress echocardiography; N, number PK, pharmacokinetic sample; RE/V, resting echocardiography/Valsalva; W, week

At Screening, subjects will undergo transthoracic echocardiography (TTE) in the supine or left lateral decubitus position. In addition to a standardized complete TTE, both resting instantaneous peak LVOT gradient (baseline) and provoked peak LVOT gradient (Valsalva maneuver) will be collected. Subjects will then undergo a standard symptom-limited exercise test (hemodynamic stress echocardiography). Subjects will be assessed systematically for

symptoms of dyspnea and/or angina. Instantaneous peak LVOT gradient will be assessed immediately post-exercise by TTE.

On Day 1, resting TTE will be performed, blood samples will be drawn for PK, and subjects will have an assessment of pVO₂, VE/VCO₂, and other variables via cardiopulmonary exercise testing (CPET). After CPET, subjects will be dosed with open-label oral MYK-461 at the investigational site and will be observed for at least 1 hour after dosing, with assessment of vital signs and ECGs at 1 hour postdose. Subjects will then be supplied with MYK-461 sufficient for QD dosing at home.

Subjects will be evaluated at the investigational site at Weeks 1, 2, 3, 4, 5, 6, 7, 8, 12, and 16. At each of these visits, resting TTE will be performed and blood samples will be drawn for PK. On study visit days, study medication will be administered at the investigational site in order to collect blood samples for PK \leq 2 hours prior to dosing. At Weeks 4, 12, and 16, hemodynamic stress echocardiography will be performed and peak LVOT gradient will be assessed. CPET will be conducted between Weeks 10 and 12 (inclusive).

Part A:

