5.5 Withdrawal and Replacement of Subjects

5.5.1 *Withdrawal from the Study*

Study participants may withdraw from further participation in the study at any time and for any reason. The degree to which a study participant withdraws can vary, and efforts will be made to collect important safety data if feasible and the study participant agrees. Study participants can:

- Withdraw from treatment and agree to participate in the Early Termination and End of Study (EOS) visits
- Withdraw from treatment and agree to participate in the Early Termination visit
- Withdraw from treatment and all follow-up

The investigator or MyoKardia may withdraw a study participant from treatment in the study for any of the following (or other) reasons:

- AE
- Noncompliance with study procedures/restrictions
- Study termination by MyoKardia

In all cases, the reason(s) for study withdrawal will be recorded in the source document and on the appropriate electronic case report form (eCRF).

5.5.2 *Replacement of Subjects*

Subjects who do not receive MYK-461 may be replaced. Subjects who drop out of the study for reasons other than AEs after receiving study medication may be replaced at the discretion of MyoKardia.

All data from subjects who receive at least 1 dose of IMP will be documented and maintained in the clinical trial database.

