11.3.1 Analysis Populations

Three analysis populations are defined in this study.

The Efficacy/PD Analysis Population is defined as all subjects who receive at least 1 dose of MYK-461 and have primary or secondary endpoint data, including a baseline value and at least one post baseline value. All efficacy and PD analyses will be performed on the Efficacy/PD Analysis Population.

The Safety Analysis Population is defined as all subjects who receive at least 1 dose of MYK-461. Safety analyses will be performed on the Safety Analysis population.

The PK Analysis Population is defined as all subjects who received at least 1 dose of MYK-461 and have detectable PK data. PK analyses will be performed on the PK Analysis Population.

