4.3.2. Efficacy Analysis Population

The Efficacy Analysis Population is defined as all subjects who receive at least 1 dose of MYK-461 and have primary or secondary endpoint data, including a baseline value and at least one post baseline value. All efficacy analyses will be performed on the Efficacy Analysis Population. Subjects in the efficacy population will be analyzed according to the planned dose combination.

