7.2.2. Treatment Compliance

Study drug compliance will be calculated for each subject by taking into account whether a subject takes all doses of study drug as instructed. The number of tablets taken will be calculated by subtracting the number of tablets returned from the number of tablets dispensed.

The overall study drug compliance (%) will be calculated by dividing the actual cumulative dose taken at all visits by the planned cumulative dose prescribed for all visits and then multiplying by 100. The overall study drug compliance will be summarized.

Summary statistics on percentage of treatment compliance as well as the number and percentage of subjects in each compliance category (<75%, 75-85%, and greater than 85% compliant) will be presented overall. Percentages will be calculated out of the number of subjects who were dosed in the Safety set. A subject is considered compliant if overall study drug compliance is greater than or equal to 80%.

8. Efficacy Analysis

All efficacy analyses will be performed on the Efficacy Analysis Population.

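### The efficacy set is worded two ways, and under either wording a dosed subject with no post-baseline value escapes the missing-counts-as-non-response rule

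*Protocol*

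**What the plan says.** All three definitions of the efficacy set require at least one dose and data on a primary or secondary endpoint. They differ in what must follow baseline.

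- Protocol synopsis, Statistical Analyses: "including a baseline value and at least one post baseline value measured during the on-treatment period".
- Protocol 11.3.1: "including a baseline value and at least one post baseline value. All efficacy and PD analyses will be performed on the Efficacy/PD Analysis Population".
- SAP 4.3.2: "including a baseline value and at least one post baseline value. All efficacy analyses will be performed on the Efficacy Analysis Population".

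The response rates sit inside this set, because SAP Section 8 opens with "All efficacy analyses will be performed on the Efficacy Analysis Population". The missing-data rule for response is in the synopsis, in protocol 11.3.5.2 and in SAP 8.2: "In case of missing data at a given visit, it will be assumed that the subject had not achieved an LVOT gradient response".

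Two further provisions decide who is affected. From Week 1 on, protocol Section 4 says "At each of these visits, resting TTE will be performed and blood samples will be drawn for PK", so LVEF, a secondary endpoint, is first due after baseline at Week 1. The Dyspnea NRS is also due then (protocol Appendix 1). For subjects who stop drug, protocol 5.5.1 offers, among other options, "Withdraw from treatment and agree to participate in the Early Termination and End of Study (EOS) visits". The Early Termination visit includes resting echo, stress echo and the NRS (protocol 9.5.6).

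**The concern.** There are two separate problems.

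First, the synopsis and the body of the same protocol do not select the same subjects. Someone who stops drug early and is assessed only afterwards belongs to the set under one wording and possibly not under the other.

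Second, the response analysis is meant to be conservative: no gradient at a visit means no response. The rule applies only to members of the efficacy set. A dosed subject who leaves before any post-baseline endpoint value is obtained, for an adverse event or any other reason, is not counted as a failure. That subject is not counted at all. At stake are the <30 mm Hg response rate (secondary) and the <10 mm Hg rate (exploratory), each reported on about 10 subjects per part.

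**Working it through.** **Who is in and who is out.** Take a dosed subject with a baseline value who stops drug in the first week.

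| Post-baseline data obtained | Synopsis | 11.3.1 and SAP 4.3.2 | Treatment in the response rate |
|---|---|---|---|
| Week 1 LVEF or NRS while still on drug | In | In | Non-responder at any stress-echo visit with no gradient |
| Only an off-drug Early Termination or later value | Depends on an undefined period | In | Under 11.3.1 and the SAP, as above; under the synopsis, possibly not counted |
| No value of any primary or secondary endpoint | Out | Out | Not counted |

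Row two turns on what counts as on treatment. I find no definition in the protocol or SAP text available. It could end at the last dose, or run on as the SAP 9.1 window for treatment-emergent events does (drug stop plus 28 days). Under the second reading an Early Termination visit soon after the last dose would still qualify.

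Row three does not depend on the clause. All three wordings exclude this subject.

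**The plan's own figures.** The documents state no expected response rate and no early-stop rate, so there is nothing of that kind to reproduce. The planned 10 per part comes from the sample-size section. Its power table does reproduce with a paired t-test on the change (n = 10, SD 35 mm Hg, one-sided 0.05): 99.4%, 95.4%, 80.4% and 51.0% for 50, 40, 30 and 20 mm Hg, against the stated >99, 95, 80 and 50. That table concerns the primary endpoint and does not bear on the response rates.

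**Size of the effect.** Let r be the number of responders and k the number of dosed subjects excluded as in row three. They have no gradient, so r is unchanged. With 10 dosed:

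- rate with all dosed as denominator: r/10
- rate with the efficacy set as denominator: r/(10 − k)
- difference: r·k / [10(10 − k)], which is never negative

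| r (assumed) | k = 0 | k = 1 | k = 2 |
|---|---|---|---|
| 3 | 30.0% | 33.3% | 37.5% |
| 5 | 50.0% | 55.6% | 62.5% |
| 7 | 70.0% | 77.8% | 87.5% |

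One exclusion adds 3/90 = 3.3 points at r = 3 and 7/90 = 7.8 points at r = 7. Two would add 3/40 = 7.5 and 7/40 = 17.5 points. For scale, the exact 95% interval is 34.8% to 93.3% for 7/10 and 40.0% to 97.2% for 7/9.

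Protocol 5.5.2 lets the sponsor replace dosed subjects who leave for reasons other than adverse events. A replacement restores the count but does not return the lost subject to the denominator.

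**The case against.** The case against is strong on scope, and most of it stands.

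- A reader might infer that every first-week stop leaves the response denominator. The documents do not support that. Under 11.3.1 and SAP 4.3.2, one LVEF or NRS value from Week 1, Early Termination or an unscheduled echo keeps the subject in, and missing gradients at Weeks 4 and 12 then count as non-response.
- A reader might infer that membership depends on staying on drug. Neither 11.3.1 nor the SAP says so. Only the synopsis could have that effect, and only under one reading of an undefined term.
- A reader might infer that protocol and SAP will report different denominators. The protocol body and the SAP agree; the synopsis is the exception. Protocol 11.3 describes its own analyses as an outline and leaves full detail to the SAP, so the SAP wording would most likely govern.
- A reader might infer that the primary model is compromised. Baseline is one of its modelled timepoints, so a baseline-only subject could enter. No gain for the Week 12 estimate from adding such a subject has been shown, and that part is dropped.

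The rates are only summarized, with no test or decision rule attached. SAP Section 5 reports the size of the safety and efficacy sets and the reasons for discontinuation, so an exclusion would be visible and an attentive reader could recompute the rate.

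Two things survive. The wording conflict is there on the page, and the row-three subject is outside all three definitions. Being able to recompute a rate does not make the reported one right.

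**Conclusion.** The point holds in a narrow form and is minor. The synopsis carries an on-treatment condition that 11.3.1 and SAP 4.3.2 lack, and this can change membership for a subject whose only post-baseline value is off drug. Separately, all three wordings remove a dosed subject with no post-baseline endpoint value, which bypasses the plan's own non-response rule and can only raise, or leave unchanged, the <30 and <10 mm Hg rates.

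The size is about 3 to 8 points per excluded subject for 3 to 7 responders out of 10 dosed. Both the responder count and the number excluded are assumptions. Only subjects with neither a Week 1 assessment (about Day 8) nor an Early Termination or later one are affected, so I assume zero or one per part; at zero there is no effect. No formal inference in the plan depends on it.

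**What to change.** 1. In the synopsis, delete the on-treatment clause so that it matches 11.3.1 and SAP 4.3.2.
2. For the <30 and <10 mm Hg response rates only, take as denominator all subjects who received at least one dose. This is the Safety Analysis Population, so no new set is needed. Count a missing stress-echo gradient at Week 4, 12 or 16 as no response at that visit. In the SAP's summary across visits, a subject with no gradient at any visit is then a non-responder.
3. Amend the statements in the synopsis, protocol 11.3.1 and 11.3.5, and SAP 4.3.2 and Section 8 that place all efficacy analyses on the efficacy set, and the population shown for Tables 14.2.1.3.A and 14.2.1.3.B. SAP Section 4 keeps stops before the Week 4 dose adjustment out of the dose columns, so the change will show in the total column.
4. Leave the MMRM population as it is.

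The cost is a few sentences and cross-references, and response rates that may be slightly less favourable. No extra data are needed.
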